11.3 Statistical Analyses

Statistical analyses will be conducted per Statistical Analysis Plan version 1.4.6.

11.4 Safety Analyses

Device-related and procedure-related adverse effects (AEs) will be tabulated and analyzed.

12 STUDY MANAGEMENT AND ADMINISTRATIVE CONSIDERATIONS

12.1 Investigator Selection

The Investigator(s) will be invited to participate in the study based on his or her medical specialty and experience conducting clinical research studies. Access to potential study subjects and the Investigator's sincere interest in this study along with expressed willingness to cooperate with the study process and requirements are also considered.

12.2 Training and Monitoring

The investigators and site research staff will be trained on the study procedures.

Investigator will allow sponsor representatives to periodically review the study documentation. Monitoring of the site will occur to evaluate the progress of the study, verify the accuracy and completeness of CRFs, assure that all protocol requirements, applicable FDA regulations and the investigator's obligations are being fulfilled and resolve any inconsistencies in the study records.

12.3 Informed Consent

The investigator is responsible for ensuring that informed consent, using an Institutional Review Board (IRB) approved informed consent document, is obtained for each subject before the performance of any protocol procedures, including administration of the study device. The informed consent document must comply with all essential elements as defined in 21 CFR 50.25 "Elements of Informed Consent" and must contain a statement that consent is freely given, the study involves research, the subject is aware of the risks and benefits of entering the study, and that the subject is free to withdraw from the study at any time. An evaluation of each candidate will be conducted by the investigator. Upon determining a subject's eligibility status, the subject will be offered the opportunity to participate in the study.

The investigator or the investigator's designee will inform all subjects regarding the purpose of the study and expected duration, as well as the potential risks and benefits that may result from participation. The subjects shall be informed by the investigator or investigator's designee that they are free to refuse participation in this clinical study. If they elect to participate, it will be made clear that they may withdraw from the study at any time without prejudicing further care.

The acquisition of informed consent will be documented in the subject's medical records, as required by 21 CFR 812.140.

12.4 Protocol Compliance

The principal investigator must comply with all terms of the protocol.

12.5 Protocol Amendments

Neither the principal investigator nor the sponsor will modify or alter this protocol without first obtaining the concurrence of the other party (with the exception of amendments which involves mitigating a medical emergency or immediate health risk to the subject). The party initiating an amendment must confirm it clearly in writing and it must be signed and dated by the sponsor and the principal investigator. IRB approval must be obtained before implementation of an amendment.

12.6 Protocol Deviation

Significant protocol deviations must be reported to the IRB according to their policies.

12.7 Study Discontinuation

Cognoa, Inc. (the sponsor) has the right to terminate this study at any time. Reasons for terminating the study may include, but are not limited to, the following: incidence or severity of adverse events in this or other studies indicates a potential health hazard to subjects; subject enrollment is unsatisfactory; number of protocol deviations is unacceptable; data recording is inaccurate or incomplete; or questionable study site compliance with ICH-E6, Good Clinical Practice.

12.8 Data Collection, Record Keeping and Storage

The principal investigator is responsible for assuring that all study records including case report forms (CRFs), informed consent forms, device accountability records, source documents (e.g., notes, medical records etc.) and other study records are complete, accurate and recorded in a timely manner. All study data will be captured on the CRFs. All data entries on the CRFs will be recorded completely, promptly, and legibly using blue or black indelible ink pen and accuracy will be ensured. The corrections on CRFs will be made only by the designated study staff. To make a correction to an entry, the data will be crossed through with a single line (the original entry should be visible) and then will be initialed and dated by the person making the correction.

The study records will be maintained in a secure location throughout the duration of the study. Upon study completion or termination, records will be kept at a secure location until at least 2 years after the last approval of a marketing application and until there are no pending or contemplated marketing applications or at least 2 years have elapsed since the formal discontinuation of clinical development of the investigational product.

12.9 Subject Confidentiality

This study preserves the confidentiality of all subjects under the Health Insurance Portability and Accountability Act of 1996 (HIPAA) Privacy Rule. The following safeguards will be in place to protect the privacy of the individuals who are the subjects of the health information to be used in the research and the confidentiality of that information:

The subjects will be informed by the investigator or the investigator's designee that their medical records will be kept as confidential as possible but may be subject to review by: (1) Cognoa, or its representative; (2) reviewing

IRB; and/or (3) by appropriate regulatory bodies (e.g. the US Food and Drug Administration (FDA), Department of Health and Human Services (DHHS) agencies).

Only pieces of personal information required for purposes of the study will be collected. The personal information will be collected and used to ensure subject eligibility for study participation, to conduct the study and to assess the results of the study as required and permitted by law. Subjects have the right to see and copy any of the information gathered about them and request changes if the information is not correct, until it is no longer kept by the investigator. Permission to use or disclose personal information, except for that has been collected and relied on may be cancelled by the subject by written notice. If the subject is withdrawn from the study, the information collected to that time may still be used to preserve the scientific integrity of the study. There is no expiration date to this authorization.

Subjects' identities will be kept confidential. Subjects will be assigned a unique study code that will not reveal the subjects' identity, and this code will be used on all study documents.

APPENDIX - STANDARDIZED MEDICAL HISTORY AND PHYSICAL FORM

HISTORY AND PHYSICAL INTAKE FORM

Subject ID	Date of Evaluation		Biological Sex  Female  Male
Child's Name (Last, First)	Date of Birth		Age (months)

HISTORY OF PRESENTING ILLNESS:

Age caregiver first became concerned about patient's development or behavior? _____

Does the child have any of the following compared to other children his/her age (Circle all that apply):

Impulsive/Overactive	Destructive	Unable to separate from parent
Short attention span/Distractible	Aggressive	Sad or Depressed
Daydreams	Wetting pants/bed	Suicidal thoughts
Classroom disruption	Bowel accidents	Eats or Mouths non-food items
Is easily overstimulated in play	Poor eye-contact	Psychiatric/emotional problems
Easily frustrated	Low self-esteem	Plays with toys abnormally
Doesn't follow directions	Isolated/withdrawn	Sexualized behavior
Oppositional/Defiant	Excessive worry/fears	Obsessions or compulsions
Sensitive to noises/ lights/ textures	Need for sameness	Difficulty making or keeping friends
Self-injurious (head bangs, bites/hits self)	Requires a lot of parental attention	Overreacts when faced with a problem
Rocking/spinning/hand flapping	More interested in things than in people	Does not show much emotion

Other problems or comments regarding infancy or early childhood development?

BIRTH HISTORY

Is child adopted?  Yes  No In foster care?  Yes  No If Yes, from what age? _____			
Mother's age during pregnancy	Father's age during pregnancy	Prenatal care received?  Yes  No	Previous pregnancies?  No  Yes: If yes, number of pregnancies _____ Number of miscarriages (if any): _____
Prescription medications used during pregnancy:			
Maternal use any of the following while pregnant:  Tobacco  Alcohol  Marijuana  Methamphetamine  Cocaine/Crack  Heroin  Methadone  Other (specify): _____			
Were there any problems during pregnancy or delivery?  No  Yes (details):			
Full term (40 wks)?  Yes  No	Birth weight: _____ (lbs) Or _____ (kg)	Birth Length: _____ (in) Or _____ (cm)	Birth Head Circ: _____ (in) Or _____ (cm)
If premature, how early? _____ weeks	Method of Delivery:  Vaginal  C-section		
If overdue, how late? _____ weeks			
Did child need any special care after delivery?  No  Yes (details):			
Health problems (feeding difficulties, poor weight gain, etc.) during infancy?  No  Yes (details):			
Maternal or Paternal Depression following the birth?  No  Yes (details):			

Additional Birth History:

DEVELOPMENTAL HISTORY:

Age of first developmental concern: months

Please note the age at which your child first did each of the following (write N/A if he/she does not do this yet):

Sat independently: _____

Walked 10 steps: _____

Said first word (other than mama/dada): _____

Put two words together (e.g. "my ball") _____

Toilet trained: Bladder _____

Bowel _____

Fed self with utensils (fork, spoon) _____

Provide an example of something your child might say:

Provide an example of how your child lets caregiver know what he/she needs?

Caregiver concern regarding child's ability to think or that learning is delayed?

No Yes, Please specify:

How old does caregiver think child seems to act? _____

History of child gross motor delays (e.g. sitting, walking, skipping, riding a bicycle, etc.)?

No Yes, Please specify:

History of child fine motor delays (e.g. drawing, writing, cutting, eating with utensils)? What any part of child's small muscle development slow?

No Yes, Please specify:

Are child's self-help skills (i.e. dressing, toileting, bathing, etc.) age-appropriate?

Yes No: Please explain:

Has child ever lost any previously acquired and well-established language, motor, self-help, or social skills?

No Yes - What age? ____ years. Please describe:

Any prior developmental evaluations through Early Intervention, Developmental Pediatrics, etc.:

PAST MEDICAL HISTORY:

Circle Any That Apply

Chickenpox Frequent ear infections Problems with ears or hearing Nasal allergies Problems with eyes or vision

Asthma, bronchitis, bronchiolitis, or pneumonia Any heart problem or heart murmur Anemia or bleeding problem

Blood transfusion HIV Organ transplant Malignancy/bone marrow transplant Chemotherapy

Frequent abdominal pain Constipation requiring doctor visits Recurrent urinary tract infections and problems

Congenital cataracts/retinoblastoma Metabolic/Genetic disorders Cancer Kidney disease or urologic malformations

Sleep problems; snoring Chronic or recurrent skin problems (eg, acne, eczema) Frequent headaches

Convulsions or seizures Obesity Diabetes Thyroid or other endocrine problems High blood pressure

History of serious injuries/fractures/concussions Dental decay

Hospitalizations/ Major Illnesses /Surgeries:

SOCIAL HISTORY

Early Intervention Services:  No Services  Current Services (Please specify in hr/week or hr/ month):	
Does the child currently attend daycare?  No  Yes (Please explain):	
Current Grade in School (if applicable):	Type of Class (mainstream or special education services):
Concerns (if any) child's current teacher has?	
Any evaluations child has received through school district (SST, Speech Evaluation, Psychoeducational evaluation, etc.):	
Has child ever had an Individual Education Plan (IEP or IFSP)?  No  Yes. If yes, reason:	
Services child CURRENTLY RECEIVES at school and how often (i.e., Resource support or specialized instruction, aide, speech therapy, occupational therapy, adaptive PE, social skills group, positive behavioral support plan, etc.).	
Any other services child has RECEIVED IN THE PAST through school.	
Please describe any major family stressors at the present time, if any?	

Please note if there is a history of any of the following (check all that apply):

 Marital discord/separation/divorce	 Parent deployed overseas/out of town for work extensively	 Financial problems
 Custody disputes	 Parent legal problems	 Parent job loss
 Birth/Adoption of another child	 Parent alcohol/ drug use	 Witness physical violence
 Severe sibling/ illness or death	 Living away from parent	 Witness sexual abuse
 Parent emotionally/mentally ill	 Other significant trauma/negative event	

If yes to any of the above, provide circumstances:

REVIEW OF SYMPTOMS

Concern	Never	Currently	In the past
Fatigue			
Sleep problems (falling asleep, staying asleep, snoring, difficulty breathing at night, etc.)			
Genetic disorder			
Head injury/brain problem (hydrocephalus, brain bleed)			
Seizures			
Headaches			
Tics, tremors, or unusual movements			
Eye or vision problem			
Ear or hearing problem			
Dental or tooth problem			
Nose and Throat problems			
Heart problem			
Heart rhythm problems			

Concern	Never	Currently	In the past
Breathing/lung problem, asthma			
GI problem: vomiting/reflux/stomach pain			
Diarrhea (loose, watery stools)			
Constipation (hard, painful stools)			
Feeding problem or use of a feeding tube			
Limited diet (picky eater):			
Kidney/bladder/genital problems			
Bone, joint, or muscle problems			
Anemia or other blood problems			
Skin conditions or birthmarks			
Endocrine or hormone problems			
Growth problems (short stature, overweight/underweight, etc.)			
Allergies			
Health concern not listed above			

Child uses any adaptive equipment (circle)?

Glasses Hearing aids Walker Wheelchair Communication device

Other:

BIOLOGICAL FAMILY HISTORY

Please note who, if any, of the child's biological relatives have had these conditions ("blood related" family members only; i.e. biological parents, siblings, aunts, uncles, grandparents)

Conditions:	Relative(s) with the condition (if 2d degree relation, specify maternal or paternal)
Autism Spectrum Disorder	
ADHD	
Learning disabilities or intellectual disability	
School failure (please explain)	
Developmental delays (speech delay, delayed walking, etc.)	
Schizophrenia or psychosis	
Depression	
Bipolar Disorder	
Anxiety or OCD	
Tics or Tourette's Disorder	
Seizures	
Genetic disorder (Down Syndrome, Fragile X Syndrome, Tuberous Sclerosis Complex, Neurofibromatosis, etc.)	
Substance abuse (alcohol, drugs, etc.)	
Other/Additional Details (Please Specify)	

Current medication(s) that child takes:

ALLERGIES:

Not Known Medication Allergies

IMAGING, LABORATORY, AND NEUROPSYCHOLOGICAL TESTING

(attach reports if available, excluding/redacting assessment portion)

Test	Yes	Don't Know	If Yes, Abnormal?
Array CGH (microarray) or Karyotype			Details:
Fragile X			Details:
Testing for Rett Syndrome (MECP2)			Details:
Whole Genome/ Exome			Details:
MRI of the brain			Details:
EEG (electroencephalogram)			Details:
Sleep Study			Details:
Audiology (Hearing) Testing			Details:

Neuropsychological Testing			Details:
Other:			Details:

PHYSICAL EXAMINATION

Height: _____ cm Weight: _____ kg Head Circumference: _____ cm
(attach growth charts if available)

CATEGORY	STATUS	IF ABNORMAL, DESCRIBE BELOW
Vital Signs	 Normal  Abnormal  Not Examined	
General Appearance	 Normal  Abnormal  Not Examined	
HEENT	 Normal  Abnormal  Not Examined	
Respiratory	 Normal  Abnormal  Not Examined	
Cardiovascular	 Normal  Abnormal  Not Examined	

CATEGORY	STATUS	IF ABNORMAL, DESCRIBE BELOW
Abdomen	 Normal  Abnormal  Not Examined	
Genitourinary	 Normal  Abnormal  Not Examined	
Musculoskeletal	 Normal  Abnormal  Not Examined	
Lymph Nodes	 Normal  Abnormal  Not Examined	
Skin	 Normal  Abnormal  Not Examined	

Neuropsychiatric: - Mental Status	 Normal  Abnormal  Not Examined	
Appearance/Behavior (e.g. level of motor activity, eye contact):
 
Apparent reaction to situation/reactivity level to sensory stimuli:
 
Speech/Language:
 
Vocalization/speech production
 
Affect (range of expressed emotions)
 
Thought Processes:
 
Thought Content:
 
Cognition:

Neurological: - Cranial Nerves	 Normal  Abnormal  Not Examined	
Neurological: - Tone, Motor & Coordination	 Normal  Abnormal  Not Examined	
Check if any abnormal movements noted:
 
 Tics  Chorea  Stereotypy

Neurological: - Reflexes	 Normal  Abnormal  Not Examined	
Neurological: - Sensory	 Normal  Abnormal  Not Examined

[figure not shown]

Protocol Number:	Q170886
Protocol Title:	Cognoa ASD Diagnosis Aid Validation Study
NCT Number:	NCT04151290
SAP Date:	Version 3.0, Dated February 3, 2020

	Plan Title: Statistical Analysis Plan Cognoa ASD Diagnosis Aid Validation Study	Document No.:
		PLN-004
		Revision: C
		Effective Date: February 3, 2020

Doc Title:	Statistical Analysis Plan version 1.4.7 Cognoa ASD Diagnosis Aid Validation Study		
Study Protocol Number:	Q170886		
Approvals			
Role on Project Team	Name	Signature	Date
Chief AI	[name]	 <small>[name] (Feb 3, 2020)</small>	Feb 3, 2020
Sr Dir Reg. and QA Affairs	[name]	 <small>[name] (Feb 3, 2020)</small>	Feb 3, 2020

Cognoa, the Study Sponsor, wants to make modifications to the clinical study protocol during the course of the clinical investigation.

The modification to the clinical protocol consists in increasing the study sample size, which will increase the statistical power of the investigation and confidence in reaching the defined primary endpoints.

The modification to the protocol does not affect

- (I) the validity of data or information resulting from the completion of the approved protocol, or the relationship of likely patient risk to benefit relied upon to approve the protocol;
- (II) the scientific soundness of the investigational plan; or
- (III) the rights, safety, or welfare of the human subjects involved in the investigation.

Enrollment in the study has increased steadily across the sites, which has triggered Cognoa's decision to increase the sample size. The cost-benefit ratio of increasing the sample size of this study balances out the risk of having to conduct another study to obtain more evidence.

This is a very low risk study, exempt from the IDE requirements. It is also a blinded study and the Sponsor has no insight on the study results. The data is being handled by Statking Clinical Services according to the Data Management Plan v1.0 dated November 5, 2019. 600 subjects have been enrolled, 217 completed their specialist visit and no adverse event has been recorded as of this date.

REVISION HISTORY

Change Request Number	Revision	Effective Date	Change
NA	C	Feb 3, 2020	Increase sample size

STATISTICAL ANALYSIS PLAN

Cognoa ASD Diagnosis Aid Validation Study

Cognoa, Inc.

Palo Alto, CA

Prepared by:

[name] - Primary Statistician
[name] - Chief AI Officer

SAP version 1.4.7

1 INTRODUCTION

1.1 Background

This statistical analysis plan is in reference to the clinical study outlined in *Cognoa ASD Diagnosis Aid Validation Study* ("the Protocol").

1.2 Study objective

To assess the ability of the Cognoa ASD Diagnosis Aid ("the Device") to aid in the diagnosis of ASD by comparing its diagnostic output with the clinical reference standard (specified in section *V. Study Procedures* of the Protocol), in terms of positive and negative predictive values, coverage, sensitivity, and specificity.

2 STUDY METHODS

2.1 Study Design

The study is a blinded, multi-site, prospective, active comparator cohort study. For more details on the design, refer to the Protocol.

All study participants and assessors will be blinded to the results of the device. Analysts at Cognoa, Inc. will be blinded to the diagnosis results for study participants and no analysis will be performed using the diagnosis results until the conclusion of the study.

Blind will remain unbroken until the completion of the study, including all data collection, at which point statistical analysis of the endpoints will be performed. For the full specification of the analysis of the endpoints, refer to section *5.1 Analysis Methods* of this document.

The device has tunable parameters, including underlying machine learning models, operational decision thresholds, and the agents involved. These elements are specified prior to the commencement of the study and cannot be changed during the study.

All aspects of the reference standard are specified prior to the commencement of the study and cannot be changed during the study. For specifications of the reference standard, refer to section *V. Study Procedures* of the Protocol.

2.2 Primary Endpoints

1. Composite endpoint consisting of:
 - a. Positive Predictive Value (PPV) of the device, greater than 65%
 - b. Negative Predictive Value (NPV) of the device, greater than 85%

2. Proportion of all subjects receiving "no result" output

The first, composite primary endpoint will be evaluated for success or failure as a group. For sample size and power analysis purposes, the overall error rate is controlled on a per-endpoint basis. For full specifications of the analysis of the primary endpoints, refer to section 5.1 *Analysis Methods* of this document. For full sample size calculations, refer to section 5.5 *Sample Size and Power Analysis* of this document.

2.3 Secondary Endpoints

1. Sensitivity to ASD of the device
2. Specificity to ASD of the device

These secondary endpoints will be analyzed by reporting the estimate of the specified metric as well as its 95% confidence interval. The trial will not be powered for rigorous statistical tests of the secondary endpoints. For full specifications of the analysis of the secondary endpoints, refer to section 5.1 *Analysis Methods* of this document.

2.4 Sample size

The sample size for the study will be 725. For full sample size calculations, refer to section 5.5 *Sample Size and Power Analysis* of this document.

2.5 Statistical Framework

The first primary endpoint evaluates whether the device meets the pre-specified performance goals. This will be determined using two-sided 95% statistical confidence intervals. Other endpoints include the reporting of a number of metrics about the device's performance using 95% confidence intervals. For full specifications of the analysis of the endpoints, refer to section 5.1 *Analysis Methods* of this document.

2.6 Mitigation of Bias

2.6.1 Verification bias:

No verification bias is expected to be present. All study participants will receive the reference standard diagnosis and be assessed by the device.

2.6.2 Selection bias:

No selection bias is expected to be present. The study enrollment criteria are set to match the intended indications for use of the device. Specifically, the parental level of concern for possible autism confirmed by the HCP and allowed age range are managed. For more details, refer to section *IV. Study Subjects of the Protocol*.

2.6.3 Spectrum bias:

No spectrum bias is expected to be present. The study design adopts open enrollment that is expected to enroll children from these relevant subgroups at the rates at which they are present in the target population:

- Children who are developing normally
- Children with ASD
- Children with other neurodevelopmental conditions such as ADHD, speech and language delay, etc.
- Children with both ASD and one or more other neurodevelopmental conditions

The proportions of children in the sample with these conditions are expected to match the proportions of children in the target population with these conditions, and the observed proportions will be reported.

2.6.4 Training bias:

No training bias is expected to be present. Every caregiver will undergo the device assessment only once, and all previous Cognoa users are excluded from the study. Therefore, no individual user will have the opportunity to change their ability with the device over the course of the study. Health Care Provider (HCP) users will be trained on using the device prior to the commencement of the study, in order to reduce the risk that a HCP changes how they use the device over the course of the study.

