4 STUDY ENDPOINTS

4.1 Effectiveness endpoints

The primary endpoints of this study are:

- (1) to achieve a composite of positive predictive value (PPV) greater than 65% and negative predictive value (NPV) greater than 85% for the device in relation to the clinical reference standard in the overall study population, and
- (2) measurement of the proportion of all children for whom the Device provides no result.

The secondary endpoints are:

- (1) sensitivity of the device in relation to the clinical reference standard in the overall study population and
- (2) specificity of the device in relation to the clinical reference standard in the overall study population.

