5 STUDY DURATION

The study is expected to last 6 months. Subjects' participation in the study is expected to last 6 weeks.

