6 STUDY DESIGN AND PROCEDURES

Primary healthcare providers who identify children at risk for developmental delay or learn of caregiver concern about developmental delay will inform caregivers about the clinical study. Caregivers may have access to a research coordinator, study website, or app (Cognoa Research app) to learn more about the study, provide consent, determine whether their child qualifies, and answer questions to test their comprehension of the study.

All subjects will undergo investigational (Cognoa assessment) and comparator diagnostic assessments for ASD using DSM-5 criteria and validating central review. Caregivers will be instructed to download the Cognoa Research app on their smartphone, set the username and password, complete a caregiver assessment about the child's behavior and development, and record two brief videos of their child. Caregivers will be given guidance on how to record videos. Both the assessment and the videos will be submitted via the Cognoa Research app. Cognoa video analysts will analyze the videos. The primary healthcare provider (HCP) will also answer an assessment about the child's behavior and development. The caregivers, video analysts, and HCPs providing inputs to the device algorithm will be blinded to each other's input.

Once the caregiver assessment, primary HCP assessment, and scored videos have been submitted, the device will generate a diagnostic output. The device output will be recorded by the Sponsor in a dedicated study data repository. The device inputs and the device output will not be shared with the referring HCP, caregivers, or

specialist clinicians performing diagnosis and review.

After the caregiver assessment has been completed and scorable videos submitted, the caregiver will be contacted by a research coordinator to schedule an appointment for a diagnostic evaluation by a specialist clinician. The specialist clinician will meet with the child and caregiver(s), conduct an assessment (which will be captured on video), and make a diagnosis of positive for ASD or negative for ASD based on DSM-5 criteria. The outcome of the diagnostic encounter may not be "uncertain" or "unknown at this time". The diagnosing clinician will also complete a standardized medical history and physical form (See Appendix), which may be completed during the diagnosing clinician visit. The standardized form and video will be sent to the Cognoa study monitor.

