7.2 Inclusion Criteria

To be included in the study, subjects must meet all of the following Inclusion Criteria:

- Caregiver must be able to read, understand and sign the Informed Consent Form (ICF).
- Caregiver or HCP concern for developmental delay.
- Female or Male, ≥ 18 to <72 months of age.
- Functional English capability in the home environment.
- Caregiver must have smartphone capabilities for downloading the Cognoa Research App (Cognoa supports iOS 10.0 and up, Android 6.0 and up).
- Participants must be willing to be videotaped during the diagnostic assessment by the specialist clinician.

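### Does the SAP's claim of no selection bias rest on an enrolment rule that the protocol does not contain?

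*SAP*

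**What the plan says.** SAP 2.6.2 states that selection bias is not expected. Its general reason is that "The study enrollment criteria are set to match the intended indications for use of the device". It then becomes specific: "Specifically, the parental level of concern for possible autism confirmed by the HCP and allowed age range are managed". For detail it refers to "IV. Study Subjects of the Protocol".

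Protocol 7.2 lists the concern criterion as "Caregiver or HCP concern for developmental delay", with age from 18 to under 72 months. The protocol summary repeats it. The intended use in Protocol 2 and the population in SAP 3 also rest on concern about developmental delay held by either the family or the provider.

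The first primary endpoint in Protocol 4.1 is a composite of PPV above 65% and NPV above 85% "for the device in relation to the clinical reference standard in the overall study population".

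SAP 1.2 and 2.1 refer to "V. Study Procedures" of the protocol for the reference standard. The current protocol has "5 STUDY DURATION" under that number, and its procedures stand under "6 STUDY DESIGN AND PROCEDURES".

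**The concern.** Two neighbouring parts of the SAP, 2.6.2 and 3, describe who enters the study in different terms, and the 2.6.2 version carries the argument that there is no selection bias. If enrolment really required a parent's autism concern confirmed by a provider, the sample would probably hold more children with ASD than one selected on either party's concern about delay. PPV and NPV both move with prevalence, so the same device would give different primary results in the two groups. A reader who took 2.6.2 literally could attach the trial's result to the wrong children. One who tried to check it against the cited protocol section would land on Study Endpoints.

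**Working it through.** **1. The concern rule, side by side**

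| Place | Concern about | Held by | Age |
|---|---|---|---|
| SAP 2.6.2 | possible autism | parent, confirmed by HCP | allowed range, no figures |
| Protocol 7.2 and summary | developmental delay | caregiver or HCP | 18 to under 72 months |
| Protocol 2, intended use | developmental delay | parent or HCP | 18 to under 72 months |
| SAP 3 | developmental delay | HCP or caregiver | 18 to 72 months |

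SAP 2.6.2 stands alone on the condition and on the logic. The other sources agree, and the operative criterion (7.2) matches the intended use (section 2). The general premise of 2.6.2, that enrolment matches the indications, is therefore true. Only the sentence that elaborates it is wrong.

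**2. Could provider confirmation come from elsewhere?** Protocol 7.1 has the primary HCP judge each subject's suitability, but against the listed criteria. None of these mentions a concern about autism or confirmation of a parent's concern. So 2.6.2 is not a paraphrase of 7.1.

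**3. Cross-references.** Protocol section 4 is Study Endpoints; subjects are in section 7, which SAP 3 cites correctly. Protocol section 5 is Study Duration; the reference standard is set out in section 6. The cited titles still identify the content.

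**4. Does any analysis use the 2.6.2 sentence?** No.
- SAP 5.1.1 to 5.1.3 work from six cell counts: device output (positive, negative, no result) by reference diagnosis.
- SAP 5.2 imputes missing reference diagnoses.
- SAP 5.3 splits by age, sex, race, ethnicity, parental education and site.
- SAP 5.4 builds its counts from a 6/63/31% output split.
- The 24% expected prevalence stands in SAP 3, beside the correct criterion.

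None of these conditions on autism concern or on provider confirmation.

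**5. Why the population matters in principle.** Inputs: prevalence 24% (SAP 3); outputs 6% positive and 63% negative, PPV 90%, NPV 92% (SAP 5.4). The implied output rates are:

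- P(+ | ASD) = 0.06 × 0.90 / 0.24 = 0.225
- P(− | ASD) = 0.63 × 0.08 / 0.24 = 0.210
- P(+ | no ASD) = 0.06 × 0.10 / 0.76 = 0.0079
- P(− | no ASD) = 0.63 × 0.92 / 0.76 = 0.7626

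Then PPV(p) = 0.225p / [0.225p + 0.0079(1 − p)] and NPV(p) = 0.7626(1 − p) / [0.7626(1 − p) + 0.210p].

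| Prevalence p | PPV | NPV |
|---|---|---|
| 15% (assumed) | 83.4% | 95.4% |
| 24% (SAP) | 90.0% | 92.0% |
| 40% (assumed) | 95.0% | 84.5% |

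The 24% row returns the SAP's own inputs. NPV equals 85% at p = 0.15 × 0.7626 / (0.15 × 0.7626 + 0.85 × 0.210) = 0.391.

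These figures show that predictive values belong to a population. They do not measure the effect of the wording. Children enter under Protocol 7.2 whatever 2.6.2 says, so the difference caused by the slip is zero in every row.

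**The case for a change.** The best case for a change is that predictive values cannot be separated from the population they come from, that the SAP contradicts itself within two consecutive sections, and that a correction before unblinding would cost a few sentences. SAP 3 also describes children seen at routine check-ups, while Protocol 7.1 allows recruitment from an investigator's database and from families who present themselves.

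The textual mismatch and the outdated section numbers stand. The rest carries little weight:

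- **Misreading is unlikely.** The correct population appears in the protocol summary, Protocol 2, Protocol 7.2 and SAP 3. The 2.6.2 sentence says only that the factors are managed; it is not set out as an inclusion criterion.
- **The check-up wording is not a contradiction.** SAP 3 names the population the sample is meant to represent; Protocol 7.1 names routes into the study. Whether the routes deliver that population is a question for the observed data, and rewording 2.6.2 would not answer it.
- **A fuller rewrite could make matters worse.** To say that PPV and NPV describe the enrolled population at its observed prevalence would be inaccurate. SAP 5.1.1 limits the primary analysis to subjects who complete the device assessment, and the denominators leave out no-result subjects. In the SAP 5.4 table that is 33 + 343 = 376 of 544 completers, from 725 enrolled. The expected prevalence among subjects with a definite output is (0.06 × 0.90 + 0.63 × 0.08) / 0.69 = 15.1%, not 24%.
- **A table of predictive values over prevalence is a poor remedy.** It assumes that output rates within ASD and non-ASD children stay fixed. A different concern rule could change the case mix, so the assumption is weakest in the very comparison at issue.

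**Conclusion.** The concern does not call for a change. The 2.6.2 sentence and the references to sections IV and V are clerical slips. Enrolment is governed by Protocol 7.2, which agrees with the intended use and with SAP 3, and the reference standard is set out in Protocol section 6. No subject, endpoint, interval, success criterion or power figure depends on the faulty sentence, so the effect on the results is nil. The context a reader needs for PPV and NPV is already planned, because SAP 2.6.3 commits to reporting the observed proportions with each condition.

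This conclusion assumes that sites enrol under Protocol 7.2 and not under the SAP's paraphrase, as is normal practice. It does not show that the sample is free of selection bias, only that this wording neither creates nor conceals any.
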